There will be no baseline preoperative cognitive-status inclusion/exclusion criteria. Our prior work suggests ~15% of Duke orthopedic surgery patients over age 60 have MCI, ~5% have dementia, and ~80% are cognitively normal. All primary analyses will be performed on patients grouped together independent of baseline cognitive status and dose level; exploratory analyses will examine effects stratified by baseline cognitive strata, dose level, and by APOE4 carrier status. In each successive 67-patient group, the 50 drug-treated patients will receive a higher CN-105 dose: 0.1 mg/kg in the first group, then 0.5 mg/kg in the second group, and then 1 mg/kg in the third group. In each case, CN-105 (or placebo) will be given IV every 6 hours (i.e. q6 h) from the first dose, which will occur within one hour of the scheduled or actual surgery start time, until just prior to hospital discharge or 3 days after surgery (up to 13 doses maximum), whichever occurs first. Each case start time will be defined by the study team as either the start of the surgery/procedure or the start of anesthesia (or the timed notes in the EMR for induction, intubation, or the start of anesthetic drug administration), or such times as planned/scheduled. If the case gets delayed by more than 6 hr and we've already given 1st dose, we will give an additional dose prior to surgery, but under no conditions will the patient be given more than 13 doses total of CN-105

We will also record noninvasive electroencephalogram (EEG) data from the scalps of these participants just before, during, and right after anesthesia and surgery. In the event that sufficient personnel or equipment are unavailable, or in the event that two MARBLE patients are having surgery at the same time, or in the event that there is insufficient time to place the EEG sensor on that patient's head before the start of surgery, the study team may not record EEG from all patients or at all points before, during, and just after surgery/anesthesia.

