7.1.3 Neurocognitive Testing, Delirium Testing, and Other Assessments

Neurocognitive testing and assessments may be performed remotely via teleconference or may be performed in-person in one of the study testing offices located in Duke South or other appropriate location preoperatively (baseline) and/or at 6 weeks +/- 3 weeks after surgery. They will also occur for any patients who have a 1 year post-operative study visit. Tests from the following standardized tests and assessments list will be utilized, which have equivalent alternate forms (to minimize test-retest practice effects) and have English, French and Spanish language versions:

- a. Hopkins Verbal Learning Test, Revised (HVLT-R) - an auditory-verbal word-list task used to assess learning, short-term recall, long-term recall and recognition memory that is co-normed with the BVMT-R (see immediately below).
- b. Brief Visuospatial Memory Test, Revised (BVMT-R) – a visual measure of constructional praxis, spatial/figure learning, short-term recall, long-term recall and recognition memory that is co-normed with the HVLT-R (see immediately above).
- c. Digit Span subtest from the Wechsler Adult Intelligence Scale, 3rd Revision (WAIS-III) – a test of immediate auditory-verbal recall and complex attention (i.e., working memory).
- d. Digit Symbol Coding subtest from the Wechsler Adult Intelligence Scale, 3rd Revision (WAIS-III) - a matching-to-sample visual scanning and visuomotor production task.
- e. Trail Making Test (TMT), Parts A & B – a test of simple visuomotor scanning and complex sequencing and set-switching executive demands.
- f. Controlled Oral Word Association Test (COWAT) – a test of lexical verbal fluency and information retrieval efficiency.
- g. Grooved Pegboard Test – a timed test of bilateral manual dexterity and motor speed.
- h. Wechsler Test of Adult Reading (WTAR) – a non-phonemic reading test used to assess crystallized pronunciation knowledge; a reliable estimate of premorbid intellectual

functioning.

- i. MoCA: used to screen for cognitive impairment.
- j. STOP-Bang brief questionnaire: to assess sleep apnea risk during one of the participants' trial visits.
- k. Visual analogue scale (VAS) pain assessment at each trial visit (preoperative, 6 weeks +/- 3 weeks postop).

Other assessments performed at both the preoperative and 6 week (+/- 3 week) postop visits may include:

- a. List of medications participants are currently taking at each trial visit.

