Cognitive Data Analysis: We will compare continuous cognitive index change scores (Newman MF et al, 2001) between patients who receive CN-105 vs placebo using a 2-sided t-test. Based on the cognitive change variance seen in MADCO-PC patients (SD=0.21), this study (with ≥ 117 CN-105 treated and ≥ 39 placebo treated patients) will provide 80% power with $\alpha=0.05$ to detect a half SD difference (i.e. 0.1 units) in CCI score between CN-105 vs placebo treated patients. Post-hoc ANOVA will determine if there are differences in cognitive index values by CN-105 dose level. We will also perform a chi-squared analysis (or Fisher’s exact test if needed) to determine whether the rate of POCD as a dichotomous outcome (defined by a 1 SD drop in any of the 4 cognitive domains we have previously studied- 1- verbal memory, 2- visual memory, 3- attention/concentration, and 4- executive function) differs between CN-105 vs placebo treated patients.

Delirium analysis: Patients will be divided into those with delirium (i.e., 1 or more positive delirium

assessments) vs those without delirium (no positive delirium assessments). We will compare delirium rates between CN-105 treated and placebo treated patients using a two-sided chi-square test. With an expected delirium rate of 40% in placebo treated patients, this study (with >117 CN-105 treated patients, and >39 placebo treated patients) will provide 80% power to detect a 25% lower absolute rate of delirium in CN-105 vs placebo treated patients. Post-hoc ANOVA testing will evaluate for differences in delirium rates between CN-105 drug dose level groups, with post-hoc pairwise comparison tests as appropriate. Additional post-hoc analyses will evaluate delirium duration and severity between CN-105 vs placebo treated patients.

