10.3 Measures to Minimize Bias

10.3.1 Enrollment/Randomization/Masking Procedures

Participants will be randomized to receive either CN-105 or placebo after they consent to participate in the trial, within 1 week prior to their index surgery. Participants will be enrolled in 1 of 3 dose cohorts (see [Table 1](#)) of 67 subjects each. An independent statistician will prepare dose stratified mixed block size randomization lists in a 3 to 1 ratio to achieve the desired distribution of drug and placebo. In each block of 67 trial participants, 50 will receive a given dose of CN-105 and 17 will receive placebo, in a double-blind fashion. CN-105 will be dissolved in normal saline, and either it or normal saline placebo will be administered as an IV drip over 15-30 minutes. Due to a clerical error by the Investigational Drug Services that prepares our drug/placebo doses, 69 patients were randomized to the first patient cohort rather than 67. Additionally, *because enrollment happens at consent, and not all patients that consent will be randomized, we will keep enrolling patients until we reach 67 consented and randomized patients in each of the last two cohorts.*

CN-105 and placebo will be prepared in identical bags labelled simply with the trial participant's number (1–203) to keep all trial staff and clinicians blinded to randomization. Only the

MARBLE Study – Protocol Version 7**PI: [name], PhD**

investigational pharmacist will have the randomization list that explains which drug (CN-105 or placebo) each participant is to receive and what dose of CN-105 or placebo will be administered every 6 hours (+/- 90 minutes) starting within 1 h before the scheduled or actual start of anesthesia/surgery and continuing until the end of postoperative day 3 (or when the participant is discharged home, whichever comes first), up to a maximum of 13 doses. Each case start time will be defined by the study team as either the start of the surgery/procedure or the start of anesthesia. In order to minimize bias, investigators conducting the laboratory assays on the CSF and blood samples will be blinded to trial group assignment during the course of the trial.

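### Delirium is compared by a valid but unadjusted chi-square; prespecified adjustment for baseline cognition and age would cost little and may add precision

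*Combined protocol and SAP*

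**What the plan says.** The delirium paragraph of section 10.1.3 reduces delirium to a yes/no outcome (any positive assessment against none) and states "We will compare delirium rates between CN-105 treated and placebo treated patients using a two-sided chi-square test". It names no covariate. The power statement beside it assumes that 40% of the placebo arm become delirious, takes 117 and 39 as the minimum arm sizes (CN-105 and placebo), and claims that the trial "will provide 80% power to detect a 25% lower absolute rate of delirium in CN-105 vs placebo treated patients".

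Section 4.1 sets the general approach: "All primary analyses will be performed on patients grouped together independent of baseline cognitive status and dose level". The same sentence goes on to plan exploratory analyses stratified by baseline cognition, dose level and APOE4 status. Section 10.2 repeats this, but mentions only cognitive status in the pooling clause. Section 10.1.3 adds a post-hoc comparison of delirium between dose levels.

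Section 4.1 sets no cognitive entry criteria and expects about 15% of patients with MCI and 5% with dementia. Section 7.4.1 records age and schedules cognitive testing before surgery. The battery in section 7.1.3 lists "MoCA: used to screen for cognitive impairment". On allocation, section 10.3.1 says "An independent statistician will prepare dose stratified mixed block size randomization lists in a 3 to 1 ratio", with 50 CN-105 and 17 placebo patients in each dose cohort. Cognition and age are not stratification factors.

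**The concern.** A mixed population with about one patient in five impaired is allocated 3:1 with 51 planned placebo patients, and balance on cognition and age is left to chance. If these variables predict delirium, the crude difference carries whatever imbalance occurs in the one trial that is run. It also misses the precision that adjustment could bring. The data will exist for most patients and the model could be fixed in advance, so any gain would come without more patients. If adjustment is considered only after unblinding, it can be attacked as data-driven.

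**Working it through.** **1. The plan's own power figure.** Inputs from section 10.1.3: 39 placebo at 40%, 117 CN-105 at 15%. Alpha 0.05 two-sided is assumed, because the delirium sentence does not repeat it.

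- Unpooled SE = sqrt(0.40×0.60/39 + 0.15×0.85/117) = 0.0851. Power = Φ(0.25/0.0851 − 1.96) = 83.6%.
- Pooled rate = (15.6 + 17.55)/156 = 0.2125. Null SE = sqrt(0.2125×0.7875×(1/39 + 1/117)) = 0.0756. Power = Φ((0.25 − 1.96×0.0756)/0.0851) = 88.4%.
- Other versions (continuity-corrected, arcsine, exact, Fisher) give 84.0% to 89.2%.

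None gives 80%. All are higher, so the statement is conservative. The 39 and 117 reflect about 20% loss by 6 weeks. Delirium is assessed mainly in hospital, so 51 vs 150 is closer to the analysis set. There, 40% vs 15% has 94.6% power (pooled). The arm of the two extra patients in cohort 1 is not stated; if both received CN-105, power is 94.7%.

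**2. Chance imbalance in cognition.** With 20% impaired (15% + 5%):

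- 150 vs 51: SE = sqrt(0.2×0.8×(1/150 + 1/51)) = 0.065, and 1.96×SE = 12.7 points. The chance of a gap above 10 points is about 12%.
- 117 vs 39: SE = sqrt(0.16×(1/117 + 1/39)) = 0.074. The chance of a gap above 10 points is about 18%.

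**3. Effect on the crude difference.** Assume impaired patients have 30 points higher delirium risk (the documents give no figure). A typical 6.5-point imbalance shifts the difference by 0.30×6.5 = 2.0 points, and a 12.7-point imbalance by 3.8. At 40% vs 20% the crude SE is sqrt(0.24/51 + 0.16/150) = 7.6 points.

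**4. Gain from adjustment.** Simulation with 1,500 trials per setting (Monte Carlo SE about 1 point near 80% power, 0.6 near 95%) and 3:1 allocation fixed within three cohorts. The adjusted test is a logistic likelihood-ratio test with cognition, age and cohort. The odds ratios (ORs) are assumptions. The effect 40% vs 20% was chosen because crude power is then about 80%. Cells show crude → adjusted power.

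| Strength (OR impaired / OR per SD of age) | 40% vs 20%, 51 vs 150 | Variance of risk difference (same setting) | 40% vs 20%, 39 vs 117 | 40% vs 15%, 51 vs 150 |
|---|---|---|---|---|
| None (1/1) | 78.3 → 77.9% | about +3% | 70.2 → 68.5% | 94.8 → 94.2% |
| Weak (2/1.3) | 79.1 → 79.1% | about −4% | 70.4 → 69.7% | – |
| Moderate (3/1.5) | 79.8 → 81.5% | about −7% | 71.9 → 72.9% | 95.2 → 95.7% |
| Strong (5/2, cohort shifts of ±0.3 log-odds) | 81.1 → 86.9% | about −15% | 69.8 → 76.3% | 94.3 → 96.6% |

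Adding cohort shifts to the moderate case gives 68.7 → 71.6% at 39 vs 117. A separate set of 3,000 trials per setting with other assumed odds ratios, at 40% vs 20% and 51 vs 150, gave adjusted power of about 80% (weak), 83% (moderate) and 85% (strong) against crude power of 78 to 80%.

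Variance reductions of 4%, 7% and 15% correspond to 201×(1/0.96 − 1) = 8, 201×(1/0.93 − 1) = 15 and 201×(1/0.85 − 1) = 35 extra patients.

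**5. Dose cohort.** The 50:17 split is fixed in each cohort, so the expected imbalance is about zero. Stratifying by cohort alone (Cochran-Mantel-Haenszel) changed power by at most about 0.5 point in every setting.

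**6. Model size.** Expected events at the plan's rates are 0.40×51 + 0.15×150 = 42.9. The model has five parameters (treatment, cognition, age, two cohort terms), so about 8.6 events per parameter.

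**The case against.** The case for leaving the chi-square alone is strong. It is prespecified, transparent and valid: in simulation under no effect it rejected in 4.0% to 6.1% of trials. Its standard error already covers chance imbalance, and the typical shift of about 2 points is small beside 7.6. Delirium is a secondary endpoint in a phase 2 safety trial. At the planned effect power is about 95%, so there is little to gain. About 43 events for five parameters is modest. Section 7.4.1 and footnote c of Table 2 list the cognitive tests, MoCA included, as ones that testing may cover, so a MoCA score is not guaranteed for every patient. All of this stands, and it makes the point an improvement to the plan, not the correction of an error.

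The exploratory analyses are a weaker answer. Stratified analyses look at effects within subgroups, and the post-hoc dose comparison looks between doses. Neither gives one treatment effect adjusted for cognition and age.

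Three stronger readings are tempting and not supported:

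- A reader might infer that chance imbalance biases the comparison. Randomisation keeps it unbiased on average.
- A reader might infer that sequential cohorts, enrolled over up to 72 months, distort the pooled test. Allocation is balanced within each cohort.
- A reader might infer that the plan disregards cognition and dose altogether. The second half of the section 4.1 sentence shows otherwise.

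**Conclusion.** The point holds as an inexpensive improvement. The main delirium test leaves out two baseline variables that are collected before surgery and not balanced by design, and no adjusted overall estimate is planned.

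The size is uncertain. Where crude power is about 80%, the gain is about nil if the covariates are weak, 2 to 3 points if moderate and about 6 if strong. At the plan's own effect with 51 vs 150, it lies between −0.6 and +2.3 points. A reader might conclude that the trial is certainly giving up precision. The documents give no prognostic strengths, and if cognition and age do not predict delirium, variance may rise by about 3%. Nor do the documents support a claim that delirium is underpowered at the planned difference, since the stated 80% is conservative.

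The imbalance figures assume that the 20% impaired, taken from the centre's orthopaedic patients, applies to the trial's wider surgical population.

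**What to change.** In section 10.1.3, make the main delirium analysis a logistic regression on treatment, one baseline cognition measure (MoCA or the baseline cognitive index, chosen now), age and dose cohort. Report the standardised risk difference with its 95% CI, and keep the chi-square as a sensitivity analysis. Dose cohort is included to match the analysis to the randomisation; it is not expected to add power.

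In sections 4.1 and 10.2, say that patients are pooled across cognitive status and dose level, with this adjustment for delirium.

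State in advance the form of each covariate, which test gives the p-value, and a simple rule for a missing baseline score, for example the mean of all patients computed blind to arm. Under no effect at 39 vs 117, the adjusted likelihood-ratio test rejected in 4.3% to 6.4% of simulated trials, against 4.6% to 6.1% for the crude test (Monte Carlo SE about 0.6), so its size should be checked once the model is fixed.

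The cost is wording: no new patients or visits. Section 10.3.2 keeps the primary statistician blinded until the data are locked, so the change can be made before unblinding. The downsides are a model that must be fixed in advance, the limited number of events, and a small loss if the covariates turn out not to be prognostic.

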4.2 Trial Endpoints

4.2.1 Primary Endpoint

The primary endpoint is to determine whether there is a significant difference in grade II or higher adverse events (AEs) between participants in each dose cohort of CN-105 vs. those who receive placebo.

4.2.2 Secondary Endpoints

1. Measure the increase in CSF inflammatory cytokines (i.e. IL-6, IL-8, MCP-1, G-CSF) from before to 24 hr after and 6 weeks +/- 3 weeks after anesthesia and surgery in patients who receive CN-105 vs placebo.
2. Measure the change in cognition (i.e. continuous cognitive change index) from before, immediately after, and 6 weeks +/- 3 weeks after surgery in patients who receive CN-105 vs placebo.
3. Measure postoperative delirium rates in patients who receive CN-105 vs placebo (using the CAM-ICU in intubated patients and the 3D-CAM in non-intubated patients).
4. To determine whether it is feasible to administer 90% of study doses within the required time window (every 6 hours +/- 90 minutes).

Exploratory Endpoints:

1. To describe the relationship between anesthetic exposure (duration, average hourly exposure, total exposure) and CSF inflammatory cytokine changes and demographics (age, sex, and race).
2. To describe the relationship between CSF changes in AD and inflammatory biomarkers, anesthetic exposure, and serum markers of metabolic and/or inflammatory status.
3. To describe the relationship between anesthetic exposure, CSF and serum biomarker changes, and intraoperative 32 channel EEG patterns.
4. Measure serum chemistries (Na, K, Cl-, HCO3-, BUN, Cr, Glucose) and blood counts (white blood cell count, hemoglobin and hematocrit, and platelet count) before, 24 hours after, and 6 weeks after anesthesia and surgery in patients who received CN-105 vs placebo.
5. Measure changes in quality of life from before to 6 weeks +/- 3 weeks after surgery in patients who receive CN-105 vs placebo (using the SF-36 instrument).
6. Measure intraoperative EEG spectral patterns, including previously observed “anteriorization” of 32-channel EEG alpha power (e.g., Giattino et al., 2017) and levels of burst suppression in patients who receive CN-105 vs placebo. If necessary due to COVID-19-related issues or other safety concerns or exigencies, 1-2 channel EEG will be performed using a BIS EEG monitor (or other appropriate frontal EEG device) rather than using our standard 32 channel EEG caps to minimize patient contact.
7. To determine if the other primary and secondary outcomes differ among patients who carry the ApoE4 allele or other genetic polymorphisms related to inflammation, neuroimmune function, metabolism, brain function, and/or AD.
8. Measure the change in CSF tau, phospho-tau, and amyloid beta from before to 24 hours (and to 6 weeks +/- 3 weeks) after anesthesia and surgery in patients who receive CN-105 vs placebo.

5 TRIAL ENROLLMENT AND WITHDRAWAL

5.1 Participant Inclusion Criteria

In order to be eligible to participate in this trial, an individual must meet all of the following criteria:

1. Age ≥ 60
2. Undergoing non-cardiac, non-neurologic surgical procedures; surgery scheduled to last > 2 hours; due to be admitted to the hospital following surgery.

Note: Informed consent will be obtained from each subject whenever possible. In situations where a subject is not competent to give informed consent, then the legally authorized representative (LAR) will provide consent on behalf of the subject. We will initially use consent of the LAR for subjects deemed not to have medical decision making capacity; however, should these subjects regain medical decision-making capacity after enrollment, they will be re-consented prior to continuation of participation in study. The PI will withdraw LAR consented subjects if they display distress, are uncooperative, or if the LAR consented subject indicates in any way that he or she does not wish to proceed with the LP and other procedures. The LAR should be present at study procedures to act as an advocate and to request withdrawal if/as needed. The subject's capacity to consent will be assessed at each research visit.

5.2 Participant Exclusion Criteria

An individual who meets any of the following criteria will be excluded from participation in this trial:

1. Inmate of a correctional facility
2. Scheduled to receive systemic chemotherapy between the time of the two cognitive testing sessions
3. Known inability to undergo LPs due to anticoagulant use, severe anxiety, or other clinical contraindication known ahead of time.
4. Inappropriate for study inclusion based on the judgement of the principal investigator.
5. If a patient undergoes major head trauma that occurs between the pre- and post-operative cognitive testing sessions, then they will be withdrawn from the study.
6. If a patient has lung, kidney, breast or prostate cancer, which tend to metastasize to bone, and the patient has imaging evidence of metastatic disease in their spinal column, the patient is excluded from the study to avoid even the theoretical risk of seeding the intrathecal space with cancerous cells.
7. Patients with existing imaging in the electronic medical record showing severe spinal stenosis will be excluded from this study due to the theoretical risk of causing myelopathy or radicular symptoms by introducing a needle into the intrathecal space.

5.3 Strategies for Recruitment and Retention

Surgical patients will initially be approached in their hospital room (if they are admitted before surgery) and asked whether they are interested in hearing about the study. If the patient is not admitted before surgery, he or she will be approached in the preoperative screening clinic, preoperative optimization of surgical health, one of the surgery clinics, or approached via a phone call by a member of the clinical care team and/or the study team using IRB approved phone script. In addition, potentially eligible patients will be identified in the electronic medical record

by a report, and those patients will be sent an automated message through Duke's MyChart application briefly describing the study and including a link to contact the study team if they are interested in participating. Per the template from the Duke MyChart recruitment team, the message will also contain a link to one of our MARBLE recruitment videos in which [name] explains the study. Patients will be consented before study activities begin.

We will enroll participants of both sexes and all ethnicities and racial groups. Based on the established literature regarding enrolling African-Americans and other historically underprivileged minority groups in research studies and to encourage trust and intrinsic human connections (Yancey et al, 2006), we will make every effort to have an African-American study coordinator or assistant contact African-American participants.

To help encourage study patient retention, study patients will be compensated \$50 at baseline and \$50 at the 6 week +/- 3 weeks follow up study visit (\$25 for the 6-week postoperative cognitive testing and questionnaire completion, and \$25 for undergoing the 6 week postoperative blood draw and lumbar puncture). Study patients will also receive up to \$12 at each study visit (consent, pre-op, 24hr, and 6 weeks +/- 3 weeks post-op) for valet and/or parking costs. Additionally, for study patients who need transportation, the study will also pay for a wheelchair accessible van or other appropriate transportation to bring them to and from Duke for study visits. If the study pays for transportation for the patient, then the patient will not receive a parking pass or parking voucher. For patients who wish to drive themselves to Duke and who say that paying for gas would be an issue, the study will provide reimbursement for gas mileage at \$0.50 per mile (up to 150 miles each way). Total possible direct subject reimbursement is thus approximately \$148 for patients who live close by and do not request gas compensation, up to \$100 for patients whose transportation is provided for by the study, or up to a theoretical maximum of \$748 for a study subject who lives 150 miles away and requests gas compensation.

Once patients are contacted via phone (submitted as separate phone script) and express interest in the study, we may email them a link to one of the following videos, which features [name] introducing the MARBLE study.

<https://www.dropbox.com/sh/blfaucno13w2u6e/AAAKcu0wjf1wdsuJsJow5aOHa?dl=0>

Because the idea of a lumbar puncture is scary for some patients, we have also created a series of videos explaining and showing an actual lumbar puncture procedure. If patients are concerned about this procedure from a safety and adverse event perspective, we can email them a link to one of the following videos that introduce the procedure.

<https://duke.app.box.com/folder/87650948771>

Furthermore, to promote continued patient engagement and interest in MARBLE, we have created a quarterly MARBLE newsletter with the intent of distributing them to all patients who have been consented and enrolled in MARBLE if possible. We will attempt to distribute this newsletter to patients via email or mailed through the postal service. In addition, we will attempt to give a physical copy of the current newsletter to all newly consented patients at their baseline visit, unless this is not possible due to the covid19 crisis or other exigencies. Each newsletter may contain the following: a brief synopsis of the study, study progress (recruitment goals and current recruitment attained), tips for a healthy brain, recent presentations/accomplishments from our research group, and staff member spotlight (a picture and job description of one of our research staff members and a quote from them on their perspective on the study).

We have also created an information tri-fold flier describing the MARBLE study that includes a brief synopsis of the study, eligibility criteria, what is involved in the study, and contact information for the PI, [name]. Flyers will be distributed at the clinics of Duke surgeons who may have eligible patients, at the anesthesia preoperative screening clinic, and at other relevant locations where potentially eligible patients will see these flyers.

